**11.3.2. Treatment Emergent Flag for Adverse Events**

Flag	Definition
Treatment Emergent	
 
• AEs will be considered emergent in the OLI, Injection and Follow-up Phases according to the classification defined in Table 3. AEs that occur in the Follow-up Phase will be considered Treatment Emergent.
 

## 11.4. Appendix 4: Data Display Standards and Handling Conventions

### 11.4.1. Reporting Process

Software	

 
The currently supported versions of SAS software version 9.4 will be used.
 
	
Reporting Area	
HARP Server	us1salx00259
HARP Compound	\ARPROD\GSK1265744\mid213199\internal_01 \ARPROD\GSK1265744\mid213199\internal_02 \ARPROD\GSK1265744\mid213199\primary_01
Analysis Datasets	

 
Analysis datasets will be created according to CDISC standards (SDTM IG Version 3.2 & ADaM IG Version 1.1.
 
	
Generation of RTF Files	

 
RTF files will be generated for all tables in Appendix 9: List of Data Displays.
 
	

### 11.4.2. Reporting Standards

General	

 
The current GSK Statistical Display Standards in the GSK Standards Library (IDSL) will be applied for reporting, unless otherwise stated (Library Location: https://spope.gsk.com/sites/DSLLibrary/SitePages/Home.aspx):           
 
4.03 to 4.23: General Principles
 
5.01 to 5.08: Principles Related to Data Listings
 
6.01 to 6.11: Principles Related to Summary Tables
 
7.01 to 7.13: Principles Related to Graphics
 
 
 
	
Formats	

 
GSK Statistical Display Principles (5.03 & 6.06.3) for decimal places (DP's) will be adopted for reporting of data based on the raw data collected, unless otherwise stated.
 
Numeric data will be reported at the precision collected on the eCRF.
 
The reported precision from non eCRF sources will follow the GSK Standard Statistical Display Principles but may be adjusted to a clinically interpretable number of DP's.
 
	
Planned and Actual Time	

 
Reporting for tables, figures and formal statistical analyses:           
 
Planned time relative to dosing will be used in figures, summaries, statistical analyses and calculation of any derived parameters, unless otherwise stated.
 
The impact of any important deviation from the planned assessment times and/or scheduled visit days on the analyses and interpretation of the results will be assessed as appropriate.
 
 
 
Reporting for Data Listings:           
 
Planned and actual time relative to study drug dosing will be shown in listings (Refer to GSK Standard Statistical Display Principle 5.05.1).
 
Unscheduled or unplanned readings will be presented within the participant's listings.
 
 
 
	

Unscheduled Visits	

 
Unscheduled visits will be assigned to a study visit using assessment windows defined in Section 11.2.1.
 
However, data summaries will only report visits that are planned assessment time points for each parameter (according to the Schedule of Activities in Section 11.1).
 
Evaluatable assessments at unscheduled visits will be used when categorizing values across visits, such as 'maximum grade during the injection phase'.
 
	
Descriptive Summary Statistics	
Continuous Data	Refer to GSK Standard Statistical Display Principle 6.06.1
Categorical Data	N, n, frequency, %
Graphical Displays	

 
Refer to GSK Standard Statistical Display Principles 7.01 to 7.13.
 
	

### 11.4.3. Reporting Standards for Pharmacokinetic Data

Pharmacokinetic Concentration Data	
Descriptive Summary Statistics, Graphical Displays and Listings	
Refer to IDSL PK Display Standards. Refer to IDSL Statistical Principle 6.06.1.
 
For continuous data:
 
 
Not quantifiable values (NQs) at the beginning of a participant profile (i.e. before the first incidence of a measurable concentration) are deemed to be zero as it is assumed that in this circumstance no drug is yet measurable in the blood.
 
For NQs at the end of the participant profile (i.e. after the last incidence of a measurable concentration): 
 
for individual plots and pharmacokinetic analyses these are dropped (set to missing) as they do not provide any useful information (and can erroneously indicate that absolutely no drug is present)
 
for summary statistics, these are set to 0 (to avoid skewing of the summary statistics)
 
 
 
Individual NQs which fall between two measurable concentrations are set to missing (individual values of this nature are assumed to be an anomaly).
 
If two or more NQ values occur in succession between measurable concentrations, the profile will be deemed to have terminated at the last measurable concentration prior to these NQs. For the purpose of individual participant plots, these NQs will be set to 0, and the subsequent measurable concentrations will be retained. For the derivation of pharmacokinetic parameters, these NQs and any subsequent measurable concentrations will be omitted (set to missing).
 
 
Note: Concentration values will be imputed as per GUI_51487 for descriptive summary statistics/analysis and summarized graphical displays only.

### 11.4.4. Reporting Standards for Liver Safety Data

#### 11.4.4.1. Liver Stopping/Monitoring Criteria

Element	Reporting Detail
General	
 
A liver monitoring event occurs when subject meets predefined liver chemistry monitoring criteria that trigger increased monitoring of the subject's liver chemistries, but no action is taken with study treatment unless liver chemistry stopping criteria are
 

Element	Reporting Detail
	
met. A liver stopping event occurs when subject meets predefined liver chemistry stopping criteria, ALT <math>\geq 3 \times \text{ULN}</math> for this study, that trigger discontinuation of study treatment and requirement of additional actions and follow up assessments to be performed. For subjects with more than one liver stopping or liver monitoring event, only data related to the earliest most severe criteria event is included in displays.
 
 
Resolved is defined as ALT <math>< 3 \times \text{ULN}</math> for 2 consecutive visits or <math>< 3 \times \text{ULN}</math> for one visit if subject discontinued and no data available. Post treatment records are included to evaluate resolution of the event.
 

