### **7.1.1. Liver Chemistry Stopping Criteria**

Study intervention will be discontinued **for a participant** if liver chemistry stopping criteria are met:

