## 2.2.      Study Objective(s) and Endpoint(s)

**Table 2      Study Objectives and Endpoints**

Objectives	Endpoints
Primary Objectives	Primary Endpoints
• To describe the PK profiles of CAB and RPV following a single intramuscular injection each of CAB LA + RPV LA administered to the lateral thigh muscle in adult healthy participants.	• Maximum observed concentration ( $C_{max}$ ) and time of maximum observed concentration ( $t_{max}$ ) in plasma • Area under the concentration – time curve from time zero to last quantifiable time point ( $AUC_{0-t}$ ) through the follow-up phase • Area under the concentration – time curve from time zero to infinity ( $AUC_{0-\infty}$ ) • Apparent terminal phase half-life ( $t_{1/2}$ ) and absorption rate constant ( $K_A$ LA)

Safety Objectives	Safety Endpoints

 
To assess safety and tolerability of CAB and RPV following repeated oral dose and single intramuscular injection in the lateral thigh of healthy participants
 
	
 
Safety and tolerability parameters including adverse events (AEs), clinical laboratory tests, electrocardiogram (ECG), and vital sign assessments
 

Secondary Objectives	Secondary Endpoints

 
To assess liver safety and tolerability of CAB and RPV following repeated oral dose and single intramuscular injection in the lateral thigh of adult healthy participants
 
	
 
Tolerability parameters (liver related adverse events) and liver chemistry abnormalities
 

Exploratory Objectives	Exploratory Endpoints

CCI

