## 5. CONSIDERATIONS FOR DATA ANALYSES AND DATA HANDLING CONVENTIONS

### 5.1. Treatment and Other Sub-Group Descriptions for Data Displays

Data display treatment descriptors with actual treatment dose will be defined as displayed in [Table 5](#). Safety events in the washout phase will be counted with events in the Oral lead-in phase. Safety events in the Follow-up phase will be counted separately from the Injection phase.

**Table 5** Study Treatment

Phase	Analysis	Treatment Group Descriptions			
		Code	Treatment Description	Treatment Description-Footnote	Column Header
Oral Lead-in	PK	A	Oral CAB 30mg tablet once daily x 4 weeks lead-in	Oral CAB 30mg=Cabotegravir 30mg PO 4 weeks lead-in	Oral CAB 30mg
		B	Oral RPV 25mg tablet once daily x 4 weeks lead-in	Oral RPV 25mg=Rilpivirine 25mg PO 4 weeks lead-in.	Oral RPV 25mg
	Safety	AB	Oral CAB 30mg + RPV 25mg tablets once daily x 4 weeks lead-in	Oral CAB 30mg + Oral RPV 25mg =Cabotegravir 30mg + Rilpivirine 25mg PO 4 weeks lead-in	Oral CAB 30mg + Oral RPV 25mg
	PK, Safety (ISRs), HO	C	Single 600mg CAB LA IM dose	IM CAB 600mg=Cabotegravir IM 600mg single dose.	IM CAB 600mg – Injection Phase; IM CAB 600mg – Follow-up Phase
		D	Single 900mg RPV LA IM dose	IM RPV 900mg=Rilpivirine IM 900mg single dose.	IM RPV 900mg – Injection Phase; IM RPV 900mg – Follow-up Phase
	Safety	CD	Single 600mg CAB + single 900mg RPV LA IM dose	IM CAB 600mg + IM RPV 900mg = Cabotegravir IM 600mg + Rilpivirine IM 900mg single dose.	IM CAB 600mg + IM RPV 900mg – Injection Phase; IM CAB 600mg + IM RPV 900mg – Follow-up Phase

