**CONFIDENTIAL**

208832

Laboratory: Urinalysis					
3.31.	Safety	UR1	Summary of Worst-Case Urinalysis Results (Discrete or Character Values) Post-Baseline Relative to Baseline by Study Phase	ICH E3 Note: Define change categories according to actual values expected from lab dataset Repeat for each study phase and overall	SAC
Laboratory: Hepatobiliary (Liver)					
3.32.	Safety	LIVER1	Summary of Liver Monitoring/Stopping Event Reporting by Study Phase and Overall	GSK Statistical Display Standard Note: See Appendix 11.4.4 for Criteria	SAC
3.33.	Safety	LIVER10	Summary of Hepatobiliary Laboratory Abnormalities by Study Phase and Overall	GSK Statistical Display Standard Note: See Appendix 11.4.4 for Criteria	SAC
ECG					
3.34.	Safety	EG2	Summary of Change from Baseline in ECG Values by Study Phase and Visit	GSK Statistical Display Standard	SAC
3.35.	Safety	EG2	Summary of ECG Values by Study Phase and Visit	GSK Statistical Display Standard	SAC
3.36.	Safety	EG1	Summary of ECG Findings by Study Phase and Visit	GSK Statistical Display Standard	SAC
Vital Signs					
3.37.	Safety	VS1	Summary of Change from Baseline in Vital Signs by Study Phase and Visit	ICH E3	SAC

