### 11.9.10. Non-ICH Listings

Non-ICH: Listings					
No.	Population	GSK Standard GSK Statistical Display Standard / Example Shell	Title	Programming Notes	Deliverable [Priority]
Subject Disposition					
25.	Screened	ES7	Listing of Reasons for Screen Failure	Journal Guidelines	SAC
26.	Screened	SD2	Listing of End of Study Record for Subjects Affected by Covid-19	Covid-19 relatedness as determined by Covid related AEs, PDs, missed visits, & Disposition	SAC
Prior and Concomitant Medications					
27.	Screened	MH2	Listing of Medical History for All Subjects		SAC
28.	Screened	CM3	Listing of Prior Medications	GSK Statistical Display Standard	SAC
29.	Screened	CM3	Listing of Concomitant Medications by Study Phase	GSK Statistical Display Standard	SAC
Adverse Events					
30.	Screened	AE8	Listing of Injection Site Reaction Adverse Events		SAC
31.	Screened	AE2	Listing of Relationship Between Adverse Event System Organ Classes, Preferred Terms, and Verbatim Text	GSK Statistical Display Standard	SAC
Laboratory Results					
32.	Screened	LIVER5	Listing of Liver Monitoring/Stopping Event Reporting	Note: See Appendix 11.4.4 for Criteria	SAC
33.	Screened	LIVER13	Listing Subjects Meeting Hepatobiliary Lab Abnormality Criteria	Note: See Appendix 11.4.4 for Criteria	SAC

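### SAP 11.4.4.1 keeps one liver stopping/monitoring event per subject, but Table 3.32 counts these events by phase, so a subject with events in two phases is shown as event-free in one of them

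*SAP*

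**What the plan says.** SAP Section 11.4.4.1 (Liver Stopping/Monitoring Criteria) sets the display rule. "For subjects with more than one liver stopping or liver monitoring event", it states, "only data related to the earliest most severe criteria event is included in displays". Nothing limits the selection to a phase. The same section gives the study's stopping criterion as ALT at or above 3 times ULN. It treats an event as resolved once ALT is below that level at two consecutive visits, or at one visit if the subject discontinued and no further data exist. It adds: "Post treatment records are included to evaluate resolution of the event".

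Two outputs report these events, and both carry a note to Appendix 11.4.4:
- Table 3.32 in SAP 11.9.4: "Summary of Liver Monitoring/Stopping Event Reporting by Study Phase and Overall".
- Listing 32 in SAP 11.9.10: "Listing of Liver Monitoring/Stopping Event Reporting".

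SAP Section 5.1 fixes the counting: "Safety events in the Follow-up phase will be counted separately from the Injection phase". Washout events are counted with the oral lead-in.

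The secondary objective in SAP Section 2.2 is "To assess liver safety and tolerability of CAB and RPV following repeated oral dose and single intramuscular injection". Its endpoints are liver-related adverse events and liver chemistry abnormalities.

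**The concern.** A one-event-per-subject rule suits an Overall column, where each subject should count once at the worst event. It does not suit columns split by phase. There, the question is whether the subject had an event in that phase, and an event in another phase should not change the answer.

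The split matters in this study. The protocol's risk table says that all suspected drug-induced liver injury so far arose on oral cabotegravir. A reader will therefore look at Table 3.32 to see which phase carries the events and whether any recur after the injection. If the selection is made across the study, a phase column can show no event for a subject who had one in that phase, and nothing in the table would signal it.

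**Working it through.** The plan states no figure for this point, so the check is to apply the rule as written and see which phase column loses an event.

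**Inputs**
- Rule: one event per subject, the earliest among those of the highest severity (SAP 11.4.4.1).
- Columns: Oral Lead-in, Injection, Follow-up, Overall (Table 3.32; SAP 5.1).
- Phase boundary: Injection runs to the date of the nominal Week 4 visit, and later events belong to Follow-up (SAP 11.3.1).
- Post-injection laboratory windows: Days 8 and 17 and Week 4 in the Injection Phase; Weeks 8, 12, 24, 36 and 52 in Follow-up (SAP 11.2.1, Table 9).
- Retention: injected participants are followed for 52 weeks and are not removed for medical reasons (Protocol 7.1).
- Oral lead-in: study intervention stops "if liver chemistry stopping criteria are met" (Protocol 7.1.1).
- Injected participants: about 15 (Protocol 10.2).

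**Step 1. All two-phase sequences.** There are 3 ordered phase pairs, and each event is either monitoring or stopping: 3 × 2 × 2 = 12 sequences. The rule keeps one event in each, so one of the two phases loses its event in 12 of 12.

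**Step 2. Remove sequences that the protocol should prevent.** An oral lead-in stopping event ends study intervention, so no injection should follow. That removes 4 sequences and leaves 8.

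| Remaining sequence | Event kept | Phase shown as event-free |
|---|---|---|
| Oral monitoring, then Injection monitoring | earlier | Injection |
| Oral monitoring, then Follow-up monitoring | earlier | Follow-up |
| Injection monitoring, then Follow-up monitoring | earlier | Follow-up |
| Injection stopping, then Follow-up monitoring | earlier | Follow-up |
| Injection stopping, then Follow-up stopping | earlier | Follow-up |
| Oral monitoring, then Injection stopping | later | Oral Lead-in |
| Oral monitoring, then Follow-up stopping | later | Oral Lead-in |
| Injection monitoring, then Follow-up stopping | later | Injection |

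The later event is dropped in 5 of the 8 and the earlier one in 3.

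**Step 3. What the visible text fully supports.** Seven of the 8 involve a monitoring event, and no monitoring threshold is visible. The eighth, Injection stopping then Follow-up stopping, needs only stated rules. For example: ALT at or above 3 times ULN at Day 17, below it at Weeks 8 and 12 (resolved), at or above it again at Week 24. The two events meet the same criterion, so the earlier is kept.

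**Step 4. Size.** One lost subject moves a phase column by 1/15 = 6.7 percentage points. Here Follow-up reads 0/15 instead of 1/15.

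**Step 5. Does another output recover it?**
- Listing 32: no. The rule speaks of displays, and the SAP's own list of data displays (Appendix 9) includes listings.
- Table 3.33 and Listing 33: only if a criterion in 11.4.4.2 is met. That section has no one-event rule, but none of its visible criteria is ALT at or above 3 times ULN alone. With ALT 3.5 and ALP 0.8 times ULN, the ratio is 3.5/0.8 = 4.4, below the 5 needed for hepatocellular injury. With bilirubin, INR and AST not raised, no visible criterion is met.
- Table 3.27: shows the maximum chemistry grade increase by phase, but does not identify a stopping event.
- Listing 17: shows every ALT value by phase and visit, again without event status.
- Adverse event displays: show it if it was recorded as an adverse event.

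**The case against.** The strongest reply is that little is lost. The rule sits under the stopping/monitoring heading, so by placement it governs Table 3.32 and Listing 32 only, and the routes in Step 5 remain open. A recurrence that also met the bilirubin or INR criterion would have to be reported as a serious adverse event (Protocol Appendix 6), and Table 3.9 summarises those by phase. The secondary objective's endpoints are served mainly by Tables 3.24 to 3.27 and 3.33, so Table 3.32 is supplementary. All of this stands.

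Two further replies carry less weight. The first is that the sentence does not say it works across the whole study, and Table 3.32 uses a sponsor standard shell (LIVER1) that cannot be seen here. The programmers may already select within phase, but the written rule names the subject as the unit and gives no phase limit. The second is that the display list is described as tentative (SAP 11.9). That makes a correction timely; it does not make the rule right.

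A reader might infer that a liver recurrence after the injection would disappear from the report, or that the rule systematically hides post-injection events. The documents support neither reading. The loss is confined to one table and one listing, and a more severe later event is the one retained, with the earlier event dropped instead. A reader might also point to a monitoring event in the oral lead-in being displaced by a stopping event after injection. That case rests on a monitoring threshold that the visible text does not give, and in it the post-injection event is kept.

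**Conclusion.** The point holds in limited form. As written, the per-subject rule in SAP 11.4.4.1 conflicts with the by-phase layout of Table 3.32. When it applies, one phase column is short by one subject, and Listing 32 does not show the missing event. The fully supported case is a stopping event in the Injection Phase that resolves and recurs at the same severity in Follow-up.

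The size is one subject in about 15. The rule touches only subjects with more than one liver event, so among healthy participants it may touch nobody. The SAP plans no formal analysis of safety data, so what is at stake is a correct count and a complete event listing.

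The conclusion assumes that the sentence is programmed literally, and that the unseen standard shell does not already select within phase.

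**What to change.** Replace the display sentence in SAP 11.4.4.1 with wording to this effect: in the phase columns of Table 3.32, use each subject's earliest most severe event within that phase; in the Overall column, use the earliest most severe event across the study; in Listing 32, show every liver monitoring or stopping event.

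Under this wording, both phases show their event in all 12 sequences. The phase columns may then sum to more than Overall, and a table footnote should say so.

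The cost is one SAP sentence and a by-phase selection step in the program. It needs no new data, no protocol amendment and no change to how participants are managed. If within-phase selection is already intended, the sentence simply records it.

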#### 11.4.4.2. Hepatobiliary Abnormality Criteria

Element	Reporting Detail
General	
 
To include ALT, ALP, Bilirubin, & INR parameters
 

ALT $\geq 3 \times \text{ULN}$ and BIL $\geq 2 \times \text{ULN}$	
 
If direct bilirubin is available (on the same date as Total Bilirubin), then direct bilirubin as a portion of total bilirubin must be <math>\geq 35\%</math> when total bilirubin is <math>\geq 2 \times \text{ULN}</math>, in order to satisfy the criteria.
 
Bilirubin value is on or up to 28 days after ALT value.
 

ALT $\geq 3 \times \text{ULN}$ and INR $> 1.5$	
 
INR value is on or up to 28 days after ALT value.
 

ALT $\geq 3 \times \text{ULN}$ and BIL $\geq 2 \times \text{ULN}$ and ALP 2 (<1%) $< 2 \times \text{ULN}$	
 
If direct bilirubin is available (on the same date as Total Bilirubin), then direct bilirubin as a portion of total bilirubin must be <math>\geq 35\%</math> when total bilirubin is <math>\geq 2 \times \text{ULN}</math>, in order to satisfy the criteria.
 
Bilirubin value is on or up to 28 days after ALT value.
 
The ALP value must occur on or up to 28 days after the ALT value.
 

Hepatocellular injury	
 
Hepatocellular injury is defined as <math>((\text{ALT}/\text{ALT ULN})/(\text{ALP}/\text{ALP ULN})) \geq 5</math> and ALT <math>\geq 3 \times \text{ULN}</math>. ALT and ALP values must occur on the same day.
 

Hepatocellular injury and BIL $\geq 2 \times \text{ULN}$	
 
Hepatocellular injury is defined as <math>((\text{ALT}/\text{ALT ULN})/(\text{ALP}/\text{ALP ULN})) \geq 5</math> and ALT <math>\geq 3 \times \text{ULN}</math>. ALT and ALP values must occur on the same day.
 
If direct bilirubin is available (on the same date as Total Bilirubin), then direct bilirubin as a portion of total bilirubin must be <math>\geq 35\%</math> when total bilirubin is <math>\geq 2 \times \text{ULN}</math>, in order to satisfy the criteria.
 
Bilirubin value is on or up to 28 days after ALT value.
 

BIL $\geq 2 \times \text{ULN}$	
 
If direct bilirubin is available (on the same date as Total Bilirubin), then direct bilirubin as a portion of total bilirubin must be <math>\geq 35\%</math> when total bilirubin is <math>\geq 2 \times \text{ULN}</math>, in order to satisfy the criteria.
 

AST $> 3 \times \text{ULN}$ and ALP $< 2 \times \text{ULN}$ and BIL $\geq 2 \times \text{ULN}$	
 
ALP and BIL values must occur on or up to 28 days after AST value.
 
If direct bilirubin is available (on the same date as Total Bilirubin), then direct bilirubin as a portion of total bilirubin must be <math>\geq 35\%</math> when total bilirubin is <math>\geq 2 \times \text{ULN}</math>, in order to satisfy the criteria.
 

Element	Reporting Detail
ALT>=X ULN and AST>=X ULN	
 
AST and ALT values must occur on the same day
 

## 11.5. Appendix 5: Derived and Transformed Data

### 11.5.1. General

Multiple Measurements at One Analysis Time Point

 
If there are multiple measurements within a time window (per Section 11.2.1), the value closest to the target day for that window will be used. If values are the same distance from the target, then the mean of the measurements (for quantitative parameters including ECG values) or the worst-case of the measurements (for qualitative parameters) will be calculated and used in any derivation of summary statistics.
 
Only planned assessment timepoints (according to Appendix 2: Schedule of Activities) will be included in data displays summarizing measurements by visit.
 
Assessments not chosen for use in summary statistics will still appear in the associated listings.
 
All applicable valid assessments, irrespective of proximity to the target study day, will be used when categorizing values across visits, such as 'maximum grade during the intervention phase' or 'at any time post-baseline', and for any algorithm that has specific rules for which observation to use (e.g. LOCF).
 

Change from Baseline

 
Post-Dose Visit Value – Baseline
 
Unless otherwise specified, the baseline definitions specified in Section 6.2 will be used for derivations for endpoints / parameters.
 

Study Day

 
The Study Day of an event (e.g., lab assessment, vital sign, ECG, start date of AE) will be derived as the number of days between the date of the event and the Intervention Phase treatment start date as follows: 
 
If date of event <math>\geq</math> start date of study treatment, then 
 
Study Day = Date of Event - Intervention Phase Treatment Start Date +1
 
 
 
If date of event <math><</math> start date of study treatment, then 
 
Study Day = Date of Event - Intervention Phase Treatment Start Date
 
 
 
Note that the start date of each phase is on Study Day 1 and the day before this is Study Day -1; i.e., there is no Study Day 0.
 
 
 

Phase Day

 
Calculated as the number of days from First Dose Date of CAB + RPV for the respective phase (based on study period classifications in Table 3):
 

OLI phase: 
 
If Assessment Date < First Dose Date of Oral CAB + RPV then 
 
Phase Day = Assessment Date – First Dose Date of Oral CAB + RPV
 
 
 
If Assessment Date <math>\geq</math> First Dose Date of Oral CAB + RPV then 
 
Phase Day = Assessment Date – First Dose Date of Oral CAB + RPV +1
 
 
 

Injection phase: 
 
If Assessment Date < Dose Date of Injection CAB + RPV then 
 
Phase Day = Assessment Date – Dose Date of Injection CAB + RPV
 
 
 
If Assessment Date <math>\geq</math> Dose Date of Injection CAB + RPV then 
 
Phase Day = Assessment Date – Dose Date of Injection CAB + RPV +1
 
 
 

Follow-up phase: 
 
If Assessment Date < Follow-up Week 4 Visit Date then 
 
Phase Day = Assessment Date – Follow-up Week 4 Visit Date
 
 
 
If Assessment Date <math>\geq</math> Follow-up Week 4 Visit Date then 
 
Phase Day = Assessment Date – Follow-up Week 4 Visit Date +1
 
 
 

